### *Secondary aim:*

Evaluation, if possible, of the effect of daily bathing with 4% CHG-containing soap on the incidence of possible and probable ventilator-associated pneumonia (VAP), bloodstream infection (BSI), central-line associated bloodstream infections (CLABSI), urinary tract infections (UTI) and catheter-associated urinary tract infections (CAUTI).

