### **Sample Size**

Sample size will be between 420 and 1000 patients. Sample size was calculated after a pre-trial evaluation of HAI. We retrospectively measured the pre-trial incidence of HAI at ICU and PC-ICU (patients admitted to ICU and PC-ICU between January, 1st and January, 31st 2015). Twenty patients out of 66 suffered from at least 1 HAI (incidence 30.3%).

By adopting an alpha error tolerance (false-positive risk) equal to 0.05, beta error tolerance (false-negative risk) equal to 0.1, power equal to 0.9, a potential reduction of HAI incidence by 10% and a percentage between 5% and 8% of potential dropouts, we calculated that a sample size of at least 410-420 patients would be required to provide sufficient power to detect significant differences. According to the Italian Law, patients with altered mentation at the admission could be directly enrolled by the physician after a clinical evaluation. At the recovery of consciousness, the patient will receive the specific paper to provide his consent or not.

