### **Data analysis**

Data will be analysed with a statistical software. Distribution of variables will be assessed by Kologorov-Smirnov deviation. Normal variables will be represented as mean +/- standard deviation, continuous non Gaussian variables will be represented as median and interquartile range, categorical variables will be represented as frequency and percentage. Comparison between groups will be performed with two-tailed t-test, Mann-Whitney test or chi-square test with Yate's correction, depending on variable distribution. Data analysis will be made by physicians blinded to the study arm.

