### **Data collection.**

We will enrol 420 to 1000 patients in up to one year. Randomisation will be done by a specific software; it will be a simple 1:1 randomisation at patient-level. To evaluate infections we will use data from the routine clinical practice; patients in the two arms will be evaluated in the standard way and without differences between the two arms.

Data will be collected with an ad hoc clinical report form (CRF); data about sex, age, demographic characteristics, comorbidities – evaluated by Charlson comorbidity index – and infections will be collected in the same above mentioned CRF.

These data will be collected and analysed by physicians blinded to the randomisation.

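### The Yates correction is valid but conservative: on the main outcome it costs 0.7 to 4.2 points of power that one changed sentence would recover.

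*Combined protocol and SAP*

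**What the plan says.** The Data analysis section says groups will be compared by "two-tailed t-test, Mann-Whitney test or chi-square test with Yate's correction", chosen by the distribution of the variable. Only the last of these, the "chi-square test with Yate's correction", suits a yes/no outcome. No test is named specifically for the main outcome, and no uncorrected or exact alternative is offered.

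The Sample Size section treats the main outcome as binary: 20 of 66 patients (30.3%) had at least one hospital-acquired infection (HAI). It sets an "alpha error tolerance (false-positive risk) equal to 0.05" and power of 0.9, and assumes "a potential reduction of HAI incidence by 10" per cent, without saying whether this is absolute or relative. It does not say whether the calculation used a continuity correction.

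The Data collection section states "We will enrol 420 to 1000 patients in up to one year" and, on allocation, "it will be a simple 1:1 randomisation at patient-level". The secondary infections are introduced with "Evaluation, if possible, of the effect of daily bathing with 4% CHG-containing soap", and no rates are given for them.

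**The concern.** The Yates correction subtracts a fixed amount from the observed difference before testing it. With a few hundred patients per arm, the uncorrected test already runs close to its nominal level at the planned risk. The correction therefore leaves part of the permitted 5% error unused, and that unused part is lost power.

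This matters most at the lower end of the planned enrolment, where power is already short and recruitment is limited to one year. The question is how large the loss is, and whether recovering it would endanger control of the false-positive rate.

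**Working it through.** **Inputs.** Control risk p1 = 20/66 = 0.303, two-sided alpha 0.05, power 0.90, 420 to 1000 patients in total, 1:1 allocation and 5% to 8% dropout, all from Sample Size and Data collection. Treated risk p2 is 0.203 (10 percentage points) or 0.2727 (10% relative).

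**The plan's own figure.** With d = p1 − p2 and p̄ = (p1 + p2)/2, the number per arm is

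n = [1.960·√(2p̄(1−p̄)) + 1.282·√(p1(1−p1) + p2(1−p2))]² / d².

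On the percentage-point reading, n = (1.960 × 0.6148 + 1.282 × 0.6107)²/0.01, about 396 per arm or 792 in total. This becomes 792/0.95 = 834 to 792/0.92 = 861 with dropout. With a continuity correction the total is 830 before dropout; a one-sided test needs 644; the relative reading needs 9380. No variant gives the stated total of 410 to 420. That figure resembles a per-arm number (396/0.95 = 417). This is a separate problem, but it sets the scale for what follows.

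**The two tests.** With D the absolute cross-product difference of the 2×2 table, m the total events and N = n1 + n2:

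- Pearson: N·D² / [n1·n2·m·(N−m)]
- Yates: N·(D − N/2)² / [n1·n2·m·(N−m)]

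Both are compared with 3.841. Size and power below come from exact enumeration of two independent binomials with equal arms and all patients analysed.

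| Quantity | Total N | Yates | Pearson | Difference (points) |
|---|---|---|---|---|
| Size at 30.3% | 420 | 3.9% | 5.0% | 1.2 |
| Size at 30.3% | 1000 | 4.3% | 5.0% | 0.7 |
| Power, 30.3% vs 20.3% | 420 | 61.6% | 65.8% | 4.2 |
| Power, 30.3% vs 20.3% | 1000 | 94.8% | 95.5% | 0.7 |
| Power, 30.3% vs 27.3% | 420 | 8.6% | 10.5% | 2.0 |
| Power, 30.3% vs 27.3% | 1000 | 16.7% | 18.4% | 1.8 |

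Differences are taken before rounding.

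**Hand check.** At 210 per arm on the percentage-point reading, the standard error is 0.0424 under the null and 0.0421 under the alternative.

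- Uncorrected: Φ[(0.1 − 1.960 × 0.0424)/0.0421] ≈ Φ(0.40) = 65.5%.
- Yates (d reduced by 1/210 = 0.0048): Φ(0.287) = 61.3%.

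The loss is about 4.25 points, in line with the exact 4.2. Averaging over simple randomisation gives losses of 4.25, 0.74, 1.91 and 1.83 points in the order of the table. The first decimal thus moves by up to about 0.2 with the method.

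**In patients.** By enumeration, Yates needs 230 per arm to match Pearson at 210, and 520 to match 500 (percentage points). On the relative reading it needs 278 and 564. This agrees with the approximation of 2/d extra per arm: 2/0.1 = 20 and 2/0.0303 = 66.

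**Secondary outcomes (rates assumed; the plan gives none).** Loss of power under Yates, relative to the replacement rule given under the fix:

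| Assumed rates | Loss at 420 (points) | Loss at 1000 (points) |
|---|---|---|
| 10% vs 6.7% | 4.5 | 4.8 |
| 5% vs 3.3% | 4.5 | 4.3 |
| 10% vs 5% | 6.5 | 2.8 |
| 5% vs 2.5% | 8.0 | 6.1 |

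**Size of the replacement rule.** Over common risks from 0.5% to 50% with equal arms, its size peaks at 5.3% at 420 (risk about 42%) and 5.4% at 1000 (risk 50%). Yates peaks at 4.2% and 4.6%. Averaged over the arm sizes that simple randomisation produces, the replacement's maximum is 5.05% at 420 and 5.03% at 1000. The worst single split checked gives 5.6% (180 vs 240, risk about 7%).

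**The case against.** The strongest reply is that nothing is broken. The plan prespecifies a recognised, valid test, and choosing between Pearson and Yates is a long-standing matter of preference. The choice does not decide whether the 90% target is met in any of the four main scenarios: only 1000 patients with a 10-point difference reaches it, with or without the correction. The extra power is bought by using more of the error allowance, and the replacement can slightly exceed 5% where Yates did not in any case scanned.

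Much of this stands. It is why the point is minor, and a sponsor that wants strict size control could reasonably keep Yates. But the excess above 5% nearly vanishes once averaged over the planned randomisation, whereas Yates stays at or below about 4.3% on the same average.

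A second objection is that an ordinary Fisher fallback would do as well: at 500 per arm with assumed risks of 2% vs 1%, it gives 23.9% power against 24.3% for mid-p. That is because the fallback is rarely triggered there. Used throughout, Fisher's test has 18.0% power in that case, close to 16.3% for Yates.

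It is also fair that the main-outcome figures apply to HAI. The Study design section speaks of sepsis as the outcome compared, and no sepsis rate is given.

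**Conclusion.** The point holds as a minor, inexpensive improvement. The planned test is valid but uses only 3.9% to 4.3% of its 5% error allowance at the planned risk. The cost is 4.2 points of power at 420 patients and 0.7 at 1000 on the percentage-point reading, or 2.0 and 1.8 on the relative reading. This is equivalent to about 20 or about 65 patients per arm respectively.

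These figures assume a 30.3% control risk, analysis of all enrolled patients and equal arms. With 8% dropout from 420 (193 per arm), the percentage-point loss is 4.3 points (57.7% against 62.0%). The secondary-outcome losses rest on assumed rates. Dropping the correction does not repair the sample-size shortfall.

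**What to change.** In the Data analysis section, before any comparison by arm, replace the corrected test with: Pearson chi-square test without continuity correction, or the two-sided Fisher mid-p test (twice the smaller one-sided mid-p value) when any expected cell count is below 5.

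With 210 per arm the fallback applies only when the pooled risk is below 5/210 = 2.4%. The ordinary Fisher test should not be the fallback: at 210 per arm and assumed risks of 2% vs 1%, power is 4.9% with Yates, 5.5% with a Fisher fallback and 9.4% with mid-p. At 500 per arm the choice of fallback hardly matters.

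The cost is one sentence, no extra patients, and the small excess over 5% shown above. If the sponsor prefers guaranteed size control, it should record that it accepts the conservatism.

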### **Data collection.**

We will enrol 420 to 1000 patients in up to one year. Randomisation will be done by a specific software; it will be a simple 1:1 randomisation at patient-level. To evaluate infections we will use data from the routine clinical practice; patients in the two arms will be evaluated in the standard way and without differences between the two arms.

Data will be collected with an ad hoc clinical report form (CRF); data about sex, age, demographic characteristics, comorbidities – evaluated by Charlson comorbidity index – and infections will be collected in the same above mentioned CRF.

These data will be collected and analysed by physicians blinded to the randomisation.

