## **Study design**

Prospective single-blinded randomized case-control study.

Study population: all patients admitted to the Intensive Care Unit (ICU) or to the Post-Cardiosurgical Intensive Care Unit (PC-ICU) of the University Hospital of Perugia will be enrolled.

These patients will be randomized in two arms using a specific software. Patients in the first arm (control arm) will undergo the usual hygiene procedures with standard soap; in the second arm (treatment arm) patients will be bathed with 4% CHG-containing soap (Neoxidina mani 4%), at least 30 ml according to the manufacturer indications (see the attached data sheet). In particular the whole body surface - except for the face - will be i) humidified

[figure not shown]
with water impregnated washcloths, ii) bathed with 4% CHG-impregnated washcloths (at least 30 ml) and, after at least 30 seconds, iii) rinsed with water-impregnated washcloths.

This product is already in use in our hospital to prepare patients before a surgical intervention. We will evaluate and compare the global incidence of sepsis in the two arms and, secondary, incidence of VAP, BSI, CABSI, UTI and CAUTI.

In addition to this, we will collect demographic data of each patients and data about comorbidities, cause of admission and infections occurred during the hospital stay.

This study is single-blind. Physicians that have to collect data, to diagnose infections and to analyse data won't be directly involved in washing procedures and they are not member of the medical staff of ICU and/or TIPOC. Moreover, only nurses that will wash patients by their own hands will know the arm in which the patient is. Both the usual soap and the Neoxidina mani 4% (with chlorhexidine gluconate 4%) have no colour nor other item than can favour their identification.

*Figure 1: Study design*

*Patients enrolment.*

Inclusion criteria: all patients aged  $\geq 18$  years old admitted to ICU or TIPOC.

Exclusion criteria:

- Age  $< 18$  years old;
- patients with burns;
- patients with known allergy to chlorhexidine and/or one of the components of Neoxidina mani 4%;
- patients with toxic epidermal necrolysis o Stevens-Johnson syndrome.
- pregnancy

Data will be collected on specific paper form and, then, analyzed using computerized methods (section "Criteria and data collection methods").

*Relative risk of the procedure and risk/benefit evaluation.*

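### The minimum of 420 patients does not give the stated 0.9 power: about 58-59% if the 10% reduction is absolute (after the planned 5-8% dropout), about 8% if it is relative

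*Combined protocol and SAP*

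**What the plan says.** The Sample Size section gives the total as a range: "Sample size will be between 420 and 1000 patients". The Data collection section repeats it with a time limit: "We will enrol 420 to 1000 patients in up to one year".

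The lower end comes from a calculation in the Sample Size section. Its control incidence is a one-month retrospective count at the two units, 20 of 66 patients (30.3%) with at least one HAI. Alpha is 0.05, and the other inputs are "power equal to 0.9, a potential reduction of HAI incidence by 10% and a percentage between 5% and 8% of potential dropouts". The section concludes that "a sample size of at least 410-420 patients would be required to provide sufficient power to detect significant differences".

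Allocation is 1:1 at patient level (Data collection). For categorical variables the Data analysis section plans a "chi-square test with Yate's correction, depending on variable distribution". The documents do not say whether the 10% is absolute or relative, or whether 410-420 is per arm or in total. Because 420 is also the lower limit of total enrolment, it is being used as a total.

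**The concern.** A control rate near 30%, a 10-point drop and 90% power usually call for several hundred patients per arm, so 410-420 in total looks too small by about half. If the reduction is relative, the shortfall is many times larger.

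The protocol permits enrolment to close at 420. A trial closed there would be reported as having 90% power. On the absolute reading its true power would be under 60%, so a real 10-point reduction would be missed about four times in ten, not one in ten. A null result would then be read as stronger evidence of no effect than it is.

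**Working it through.** **Inputs.** Control 0.303; alpha 0.05, taken as two-sided; power 0.9; dropout 5-8% (all Sample Size). 1:1 allocation (Data collection). Yates-corrected chi-square (Data analysis). The intervention rate is 0.203 if the 10% is absolute and 0.303 × 0.9 = 0.2727 if relative.

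**Step 1. Try to reproduce 410-420, absolute reading.** The pooled two-proportion formula per arm, with mean rate p̄ = 0.253, is

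n = [1.960·√(2p̄(1−p̄)) + 1.2816·√(p1(1−p1) + p2(1−p2))]² / (p1−p2)²

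= [1.960 × 0.6148 + 1.2816 × 0.6107]² / 0.01 = 395.1 per arm.

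- Unpooled variance: 391.9 per arm.
- Continuity-corrected, n/4 × [1 + √(1 + 4/(n × 0.1))]²: 414.8 per arm.
- Total after dropout, 2n/(1−d): pooled 790.2/0.95 = 832 to 790.2/0.92 = 859; corrected 829.7/0.95 = 873 to 829.7/0.92 = 902.

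The plan's figure is not reproduced as a total. Weaker targets do not rescue it: one-sided 0.05 with power 0.9 needs about 644 in total before dropout, and one-sided with power 0.8 still needs about 462-466.

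**Step 2. Where 410-420 may come from.** Per arm after dropout, the unpooled formula gives 412.5 (5%) to 426.0 (8%) and the pooled formula 415.9 to 429.4. The 5% end falls inside 410-420, which suggests a per-arm number used as a total. Another route is possible: a one-sample formula against a fixed 30.3% gives 200.6, which doubled and divided by 0.95 is 422. That treats the control rate as known, so it does not justify the total either. The documents do not settle the origin.

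**Step 3. Power of the planned test, absolute reading.** All pairs of event counts in two equal binomial arms were enumerated. The probability was summed over pairs where N·max(|ad−bc|−N/2, 0)² / (n1·n2·m·(N−m)) exceeds 3.84. Here a, b, c, d are the cells of the two-by-two table, n1 and n2 the arm sizes, N their sum and m the total events.

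| Randomised | Evaluable per arm | Yates | Uncorrected |
|---|---|---|---|
| 420, 8% dropout | 193 | 57.7% | 62.0% |
| 420, 5% dropout | 200 | 59.3% | 63.6% |
| 420, none | 210 | 61.6% | 65.8% |
| 792, 8% to 5% | 364-376 | 85.8-86.9% | 87.6-88.7% |
| 1000, 8% to 5% | 460-475 | 92.9-93.7% | 93.9-94.5% |

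The 792 is 66 × 12, one year at the pilot rate if every admission is enrolled.

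Hand check at 193 per arm by normal approximation: (0.1 − 1/193 − 1.960 × 0.6148/√193) / (0.6107/√193) = 0.0081/0.0440 = 0.18, which gives power of about 57%.

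**Step 4. Relative reading.** The pooled formula gives 4,690 per arm and the corrected one 4,756, so about 9,900-10,300 in total after dropout. Yates power is 8.2-8.4% at 420 and 15.5-16.0% at 1000, both after dropout.

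**Step 5. Uncertainty in the pilot rate.** The exact 95% interval for 20/66 is 19.6% to 42.9%. For a 10-point drop with 193-200 evaluable per arm, Yates power runs from 76-78% at a control rate of 19.6% to 49-50% at 42.9%. It does not reach 90% in that interval.

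**The case against.** **420 is a floor.** The plan says at least 410-420. If a full year of admissions came in at 66 a month, 792 patients would give about 86-87% power. This stands: the four-in-ten miss rate applies only if enrolment ends at the minimum. But the plan permits that ending and calls it sufficient.

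**Accrual is uncertain.** The yearly figure rests on one January count. Its exact Poisson 95% interval is 51 to 84 a month, about 612 to 1008 a year, which includes totals above 873-902. So the documents do not establish that a one-year trial must fall short of 90%.

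**The loss may come from Yates or dropout.** Only in small part: the uncorrected test with no dropout has 66% power at 420. Deducting dropout is fair because the plan lists it among the inputs behind 410-420.

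**The endpoint is assumed.** The figures use patients with at least one HAI, as the sample-size calculation does. The Study design section speaks of comparing the global incidence of sepsis, for which no planning rate is given. The recalculation shares this dependency with the plan's own calculation.

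**A stronger reading does not hold.** From a range of 420 to 1000, a reader might infer that enrolment may stop on results and that type I error is inflated. The documents do not support this. All admitted patients are to be enrolled, accrual is capped at one year, and "Data will be collected on specific paper form and, then, analyzed using computerized methods". No interim look or results-based stop is described (Figure 1 is not shown). A range around uncertain one-year accrual is the plain reading. What remains is narrower: no visible sentence fixes where in the range enrolment ends or says the arms are compared once.

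**Conclusion.** The claim that 410-420 patients in total give 0.9 power is wrong on either reading of the 10% reduction. On the absolute reading about twice as many are needed: 832-859, or about 873-902 to match the Yates test. On the relative reading no total in the permitted range comes near 90%.

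This assumes a two-sided 0.05 test, equal arms, the 30.3% control rate and a patient-level comparison of at least one HAI. Non-reproduction of the stated total does not depend on Yates, dropout or sidedness. The per-arm explanation is probable but remains an inference. The missing stop sentence is a secondary reporting gap and does not show inflated type I error.

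**What to change.** In the Sample Size section:

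- State whether the 10% is absolute or relative, and whether 410-420 is per arm or in total.
- Replace the claim that 420 gives 0.9 power with the power of the Yates test. On the absolute reading, after 5-8% dropout, this is about 58-59% at 420, about 86-87% at 792 (one year at 66 admissions a month, all enrolled) and about 93-94% at 1000.

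As a secondary change, in both the Sample Size and Data collection sections, replace the range with one stop, for example: *Enrolment closes on [fixed date] or when [one number, set in advance] patients have been randomised, whichever comes first, whatever the results. The arms are compared once, after follow-up of the last patient is complete.*

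Both changes are wording only, and no added enrolment is required. The sponsor has to state a less favourable power and gives up discretion over when to stop. Keeping 0.9 on the absolute reading is a separate choice; the roughly 873-902 it needs already lie within the permitted range.

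### One year at the only admission rate in the plan is expected to give about 777-792 patients at most: 1000 is optimistic, and the stated 90% power is not expected anywhere between 420 and that figure

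*Combined protocol and SAP*

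**What the plan says.** The Data collection section sets both size and duration: "We will enrol 420 to 1000 patients in up to one year". The Sample Size section repeats the range and bases the calculation on a retrospective count of "patients admitted to ICU and PC-ICU between January, 1 st and January, 31 st 2015". Of these, "Twenty patients out of 66 suffered from at least 1 HAI (incidence 30.3"%). The other inputs are an alpha of 0.05, 90% power, dropout of 5-8%, and an effect worded as "a potential reduction of HAI incidence by 10"%. From these the section derives a minimum of 410-420 patients.

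The Data analysis section names a "two-tailed t-test, Mann-Whitney test or chi-square test with Yate's correction". The Study design section limits enrolment to the same two units. No section projects accrual, gives another admission figure, or says what decides where between 420 and 1000 enrolment stops.

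**The concern.** Size, duration and power are stated separately and never checked against each other. The month that supplies the event rate also implies a patient flow, and a year of that flow falls short of 1000. It also falls somewhat short of the total that the protocol's own inputs require for 90% power.

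With no stopping size within the range, the calendar is likely to fix the final number. A reader who takes the text at face value would expect 90% power from 420 patients upwards. If the trial closes near 420, a null result would say much less than the protocol implies.

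**Working it through.** **Inputs.** From Sample Size: 66 patients in 31 days, 20 with HAI (p1 = 20/66 = 0.303), alpha 0.05, power 0.90, reduction 10%, dropout 5-8%. From Data collection: 1:1 allocation, at most one year. From Data analysis: two-sided testing and Yates correction. My assumptions: the 10% is absolute (p2 = 0.203), the outcome is the proportion with at least one HAI, and dropouts do not contribute to the analysis.

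**1. The plan's 410-420.** Per arm, with pooled variance under the null:

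n = [1.960·√(2·p̄(1−p̄)) + 1.282·√(p1(1−p1) + p2(1−p2))]² / (p1−p2)², with p̄ = 0.253

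n = (1.960 × 0.6148 + 1.282 × 0.6107)² / 0.10² = (1.2050 + 0.7827)² / 0.01 = 395.1 per arm.

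- Per arm after dropout: 413-417 at 5% and 426-431 at 8%, depending on the variance formula and rounding. This is within about 3% of 410 and 420.
- Total after dropout: 2 × 395.1 / 0.95 = 832 and 2 × 395.1 / 0.92 = 859. Rounding up to 396 per arm first gives 834 and 861.
- With continuity correction: 415 per arm, 830 in total, and about 873-903 after dropout.

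As a total, 410-420 is not reproduced by any two-arm variant tried. Even one-sided testing at 80% power without dropout needs about 461-466. A relative 10% reduction (30.3% to 27.3%) would need about 9,400 before dropout. The close per-arm match supports the absolute, two-sided reading.

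**2. One year of admissions.**

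- By days: 66 × 365/31 = 777. By months: 66 × 12 = 792.
- For 1000 in a year: 1000/12 = 83.3 per month, 26% above 66. At 66 per month: 1000/66 = 15.2 months.
- For 420: 420/66 = 6.4 months.
- Exact Poisson 95% interval on a count of 66: 51.0 to 84.0. Per year this is 601-989 by days or 613-1008 by months.

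**3. Power at the sizes that can be enrolled.** With m = N(1−d)/2 analysed per arm and Δ = 0.10:

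power = Φ[(Δ√m − 1.960 × 0.6148) / 0.6107]; for Yates, replace Δ by Δ − 1/m.

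| Enrolled | Dropout | m | Power | With Yates |
|---|---|---|---|---|
| 420 | 5% | 199.5 | 0.633 | 0.589 |
| 420 | 8% | 193.2 | 0.619 | 0.573 |
| 777 | 5% | 369.1 | 0.880 | 0.862 |
| 777 | 8% | 357.4 | 0.869 | 0.850 |
| 792 | 5% | 376.2 | 0.885 | 0.868 |
| 792 | 8% | 364.3 | 0.875 | 0.857 |
| 1000 | 5% | 475.0 | 0.945 | 0.936 |
| 1000 | 8% | 460.0 | 0.938 | 0.928 |

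If a further 10% of admissions were excluded or refused (an assumption; the protocol gives no figure), 699-712 would be enrolled. Power would then be 0.832-0.850, or 0.808-0.829 with Yates.

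**The case against.** **The range is not contradicted.** 1000 is an upper cap and one year is an upper limit on time. The projection of 777-792 lies inside 420-1000, and 420 is reached in about six and a half months. This stands: the sentence is optimistic at its upper end, not self-contradictory.

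**One month is thin evidence.** A reader might infer that 1000 cannot be reached in a year, or that 90% power will fail. The documents support neither. The 66 is a denominator for an incidence, not an accrual forecast. The by-months interval (613-1008) just includes 1000, and both intervals include 832-861, which needs only about 69 to 72 patients a month. What can be said is that neither is expected on the figure given. The sponsor already relies on the same month for the 30.3% event rate.

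**The shortfall near 780-790 is small.** It is 1.5 to 3 points without Yates and about 3 to 5 with it. A baseline of 28% with the same 10-point reduction would bring uncorrected power to 0.89-0.90. This stands for the top of the reachable range. It does not help at 420, where the shortfall is about 27 to 28 points, or 31 to 33 with Yates.

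**The power gap comes from the sample size, not the calendar.** Largely true. The protocol ties 90% to 410-420, which the units can easily supply. The year becomes a constraint only once that figure is corrected to 832-861, so the two points have to be settled together.

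**Conclusion.** The point holds as a mismatch between expected enrolment and stated power. About 777-792 patients is the most to expect in a year on the protocol's only flow figure, against 832-861 needed for 90% power after dropout (873-903 with continuity correction). Of the two ends of the range, the minimum matters more: 420 gives about 62-63%, while a full year gives about 87 to 88.5%, each lower with Yates.

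This rests on January 2015 being typical, an absolute 10-point reduction from 30.3%, and two-sided testing. The Sample Size section does not state sidedness; a one-sided test would need 678-700 (720-744 with continuity correction), which a year could supply, but the Data analysis section points to two tails. The annual figure also assumes that every admission is enrolled. The protocol does not say whether the 66 already reflect the exclusion criteria.

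**What to change.** Make Sample Size and Data collection carry the same figures:

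- State power across the range that can be enrolled: about 62% at 420 and about 87-88% at 780-790, lower with Yates or after exclusions and refusals.
- Say that 420 does not give 90% power, and that the inputs require about 832-861 in total after dropout (about 873-903 with continuity correction).
- Either give about 780-790 as the expected one-year enrolment, naming the single month behind it, or keep 1000 and state about 15 months or more.

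Lowering only the cap to about 790 and quoting 85-88% power is not enough. With 420 left as an unqualified minimum, a trial that stopped there would comply with the text at about 62% power.

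The cost is wording in two sections and a less favourable stated power. Keeping 1000 also means a longer enrolment period.
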